6.0 STUDY DESIGN AND DESCRIPTION

6.1 Study Design

This is a phase 3, multicenter, randomized, double-blind, parallel-group study to evaluate the efficacy and safety of TAK-491 compared with valsartan over an 8 week treatment period in Chinese subjects with essential hypertension (trough, sitting clinic SBP \geq 150 and \leq 180 mm Hg on Day 1). This study will be conducted in China at approximately 20 to 25 sites and will include approximately 600 randomized subjects.

Before initiation of treatment, all subjects will participate in a 2-week, single-blind, placebo run-in period (Days -14 to -1). Subjects who have not received antihypertensive treatment within 28 days before screening can be entered into the run-in period as soon as all inclusion and exclusion criteria, including laboratory results, have been verified. Subjects taking previous antihypertensive agents will be required to participate in a 3-week washout/placebo run-in period (Days -21 to -1). If the subject's previous antihypertensive treatment includes amlodipine or chlorthalidone, then the washout/placebo run-in must be extended to 4 weeks (Days -28 to -1). Screening (Visit 1) will be scheduled before the washout/run-in period begins so that laboratory test results can be reviewed and subject eligibility can be confirmed before other treatments are stopped or placebo is initiated. At Day -14 (Visit 2), subjects will receive the first dose of single-blind placebo in clinic.

[figure not shown]
At Day 1 (Visit 5), eligible subjects will be randomly assigned to one of the following 3 groups with a 1:1:1 ratio:

- TAK-491 40 mg QD.
- TAK-491 80 mg QD.
- Valsartan 160 mg QD.

Subjects will be given the first dose of randomized study drug in the clinic at Day 1 (Visit 5). The last dose of randomized study drug will be taken the day of Week 8 visit (Visit 9). End of study assessment will be taken at Week 8/Early Termination (Visit 9). All subjects who receive study drug (placebo or double-blind) will be required to have a follow-up telephone call at approximately 14 days after the last dose.

A schematic of the study design is included as Figure 6.a.

V=visit, N/A=not applicable, D=day, HTN=hypertension, Wk=week, ET=Early Termination.

- (a) The Screening Visit should be scheduled before the washout/run-in period begins so that laboratory tests results can be reviewed and subject eligibility can be confirmed before other treatments are stopped or placebo is initiated.

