7.1 Inclusion Criteria

Subject eligibility is determined according to the following criteria:

- 1. The subject is treated with antihypertensive therapy and has a post-washout mean sitting clinic SBP ≥150 and ≤180 mm Hg on Day 1; or the subject has not received antihypertensive treatment within 28 days prior to Screening and has a mean sitting clinic SBP ≥150 and ≤180 mm Hg at the Screening Visit and on Day 1.
- 2. The subject is a man or woman aged 18 years or older.
- 3. In the opinion of the investigator, the subject is capable of understanding and complying with protocol requirements.
- 4. The subject or, when applicable, the subject's legally acceptable representative signs and dates a written, informed consent form and any required privacy authorization prior to the initiation of any study procedures.
- 5. A female subject of childbearing potential* who is sexually active with a nonsterilized* male partner agrees to use routinely adequate contraception* from signing of informed consent through 30 days after last study drug dose.

*Definitions and acceptable methods of contraception are provided in Section 9.1.9 Contraception and Pregnancy Avoidance Procedure and reporting responsibilities are defined in Section 9.1.10 Pregnancy.

- 6. The subject has clinical laboratory test results (clinical chemistry, hematology, and complete urinalysis) within the reference range for the testing laboratory or the investigator does not consider the results to be clinically significant.
- 7. The subject is willing to discontinue current antihypertensive medications on Day -21 or on Day -28 if the subject is on amlodipine or chlorthalidone.

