9.1.9 Contraception and Pregnancy Avoidance Procedure

From signing of informed consent, throughout the duration of the study, and for 30 days after last dose of study medication, female subjects of childbearing potential* who are sexually active with a nonsterilized male partner** must use adequate contraception. In addition they must be advised not to donate ova during this period.

*Females NOT of childbearing potential are defined as those who have been surgically sterilized (hysterectomy, bilateral oophorectomy or tubal ligation) or who are postmenopausal (eg, defined as at least 1 year since last regular menses with an FSH >40 IU/L or at least 5 years since last regular menses, confirmed before any study medication is implemented).

**Sterilized males should be at least 1 year postvasectomy and have confirmed that they have obtained documentation of the absence of sperm in the ejaculate.

An acceptable method of contraception is defined as one that has no higher than a 1% failure rate. In this study, where medications and devices containing hormones are included, the only acceptable methods of contraception are:

Barrier methods (each time the subject has intercourse):

Intrauterine devices (IUDs):

Hormonal contraceptives:

- Male condom PLUS spermicide. •
- Cap (plus spermicidal cream or jelly) PLUS male condom and spermicide.
- Diaphragm (plus spermicidal cream or jelly) PLUS male condom and spermicide.
- Copper T PLUS condom Implants. or spermicide.
- Progesterone T PLUS condom or spermicide.
- Hormone shot/injection.
- Combined pill.
- Minipill.
- Patch.
- Vaginal ring PLUS male condom and spermicide.

Subjects will be provided with information on acceptable methods of contraception as part of the subject informed consent process and will be asked to sign a consent form stating that they understand the requirements for avoidance of pregnancy and donation of ova during the course of the study.

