 - that personal information (including personal health information) may be added to Takeda's research databases for purposes of developing a better understanding of the safety and effectiveness of the study medication(s), studying other therapies for patients, developing a better understanding of disease, and improving the efficiency of future clinical studies;
 - d) that subjects agree not to restrict the use and disclosure of their personal information (including personal health information) upon withdrawal from the study to the extent that the restricted use or disclosure of such information may impact the scientific integrity of the research; and

- e) that the subject's identity will remain confidential in the event that study results are published.
- 25. Female subjects of childbearing potential (eg, nonsterilized, premenopausal female subjects) who are sexually active must use adequate contraception (as defined in the informed consent) from Screening and throughout the duration of the study. Regular pregnancy tests will be performed throughout the study for all female subjects of childbearing potential. If a subject is found to be pregnant during study, study medication will be discontinued and the investigator will offer the subject the choice to receive unblinded treatment information.
- 26. A statement that clinical trial information from this trial will be publicly disclosed in a publicly accessible website, such as ClinicalTrials.gov.

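### The consent elements in Protocol Appendix C (item 25) end the contraception requirement with the study, while the protocol body runs it to 30 days after the last dose

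*Protocol*

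**What the plan says.** The eligibility rule, Protocol Section 7.1 criterion 5, asks a woman of childbearing potential who is sexually active with a nonsterilized male partner to agree to contraception "from signing of informed consent through 30 days after last study drug dose". Section 9.1.9 sets the same period: "From signing of informed consent, throughout the duration of the study, and for 30 days after last dose of study medication". Section 9.3.9 has the follow-up call counsel her on the same 30 days.

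Appendix C lists the information to be given to every subject at consent. Its item 25 says that sexually active women of childbearing potential "must use adequate contraception (as defined in the informed consent) from Screening and throughout the duration of the study". It gives no period after the last dose.

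The two places also describe the group differently. Item 25 begins "Female subjects of childbearing potential (eg, nonsterilized, premenopausal female subjects" and closes the bracket there. Section 9.1.9 works from the other side, by saying who is not of childbearing potential. For menopause its example is "at least 1 year since last regular menses with an FSH >40 IU/L or at least 5 years since last regular menses", with the status "confirmed before any study medication is implemented".

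**The concern.** Appendix C is the template from which consent forms are written. Section 15.2 makes the investigator responsible for preparing the form, subject to sponsor and ethics committee approval, and about 20 to 25 sites are planned. A site that follows item 25 faithfully would produce a form whose contraception period is shorter than the one the same woman must agree to under criterion 5. At stake is whether participants are told the full period at consent, for a precaution that the protocol body treats as extending past the last dose.

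The description of childbearing potential raises a similar, weaker question: a woman who stopped menstruating between 1 and 5 years ago may be read differently in the two places. Where Section 9.1.9 relies on an FSH value, the reader also expects to find where that value comes from.

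**Working it through.** No sample size, power or error rate enters here. The check compares current passages, with one subtraction.

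**Start of the period.** Section 9.1.9 and criterion 5 start at signing of consent, and item 25 starts at Screening. Consent is obtained at Screening (Visit 1), so the starts agree in practice.

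**End of the period.** Section 9.1.9 names the duration of the study and then, as a separate addition, "and for 30 days after last dose of study medication". Item 25 has the first part and lacks the second. Since 9.1.9 lists the two separately, the 30 days cannot safely be read into item 25.

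**Size of the gap.** Item 25 does not define when the study ends, so two readings are shown. Days are counted from the last dose.

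- The study ends at the last scheduled contact. Under Section 6.1 all dosed subjects are "required to have a follow-up telephone call at approximately 14 days after the last dose". Gap = 30 − 14 = 16 days, approximately.
- The study ends at the Week 8 visit. Section 6.1 puts the last dose on that day. Gap = 30 − 0 = 30 days.

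**Who is affected.** Under criterion 5 and 9.1.9 the duty falls on women of childbearing potential who are sexually active with a nonsterilized male partner. The documents give no count of them. On partners, item 25 is the broader text, since it says only that the woman is sexually active.

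**Description of childbearing potential.** Take an unsterilized woman 1 to 5 years past her last regular menses, with no FSH result above 40 IU/L. She meets neither limb of the postmenopausal example in 9.1.9, so she remains of childbearing potential there. In item 25 she could be taken to fall outside the word premenopausal. Both texts are introduced as examples, so this is a possible reading and not a necessary one.

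**Source of FSH.** FSH is not in Table 9.a, the Screening procedures (Section 9.3.1), the Appendix A schedule or SAP Table 7.b. For women of childbearing potential these list only serum and urine hCG.

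**Timing of the mismatch.** Appendix F shows that Section 9.3.9 already carried the 30 days before Amendment 4, and that the amendment changed only the second and fourth paragraphs of 9.1.9. The FSH and 5-year wording did come with Amendment 4. The amended hCG schedule appears in Appendix A, Table 9.a, the visit sections and the SAP schedule.

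**The case against.** The strongest reply is that nobody is classified, tested or enrolled from Appendix C. Eligibility, pregnancy testing and withdrawal run from Sections 7.1 and 9.1.9 and Appendix A, and on the period those sections agree. Item 25 is one item of information to be provided. It does not limit what else the form may say, and the form is not among the documents. The 30 days also reach the woman by other routes: her agreement under criterion 5, contraception guidance at every numbered visit, and counselling at the follow-up call. This stands as mitigation, but it does not remove the conflict. Item 25 does defer to the consent form, but the deferral attaches to what counts as adequate contraception and not to how long it lasts. A woman must agree to 30 days in order to be eligible, while the listed consent content describes less.

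On FSH, the reply is that a missing value leaves a woman 1 to 5 years past menses in the childbearing group under 9.1.9, with its tests and precautions. The protocol does not exclude a result from outside the central laboratory, and the 5-year limb needs no FSH. All of this stands and makes the FSH gap secondary.

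A reader might infer that Amendment 4 introduced the 30-day period and failed to carry it through, or that its pregnancy-test changes never reached the schedule. The documents support neither: the period is older than the amendment, and the hCG changes are in place.

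**Conclusion.** The end-date conflict holds on current text. Item 25 is shorter than criterion 5 and Sections 9.1.9 and 9.3.9 by about 16 days or by 30 days, depending on when the study is taken to end. It concerns women of childbearing potential who are sexually active with a nonsterilized male partner, in a number that the documents do not give.

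The description of childbearing potential and the source of FSH are lesser loose ends. The first rests on one possible reading of an example. The second is that no scheduled test supplies the value, not that the criterion cannot be applied.

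A reader might go further and conclude that women in this trial did consent to a shorter period, or were misclassified and left untested. The documents do not show this: the signed forms are not available, and classification follows 9.1.9. The point is an inconsistency in participant information, with no effect on power, type I error or the primary analysis.

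**What to change.** Reconcile Appendix C item 25 with Section 7.1 criterion 5 and Section 9.1.9, so that all three give the same end date and describe childbearing potential in the same way. Make Section 9.1.9, Table 9.a and Appendix A consistent on where any FSH value comes from, whether as a study test or as an outside record. Which period, definition and source apply is for the sponsor's medical lead to decide.

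The cost is appendix wording and a consent template update at the next amendment, with a check of site forms already in use. If FSH is made a study test, the laboratory table and the schedule change as well, and SAP Tables 7.b and 4.a should follow. No analysis needs to change.

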Appendix D Investigator Consent to Use of Personal Information

Takeda will collect and retain personal information of investigator, including his or her name, address, and other personally identifiable information. In addition, investigator's personal information may be transferred to other parties located in countries throughout the world (eg, the United Kingdom, United States, and Japan), including the following:

- Takeda, its affiliates, and licensing partners.
- Business partners assisting Takeda, its affiliates, and licensing partners.
- Regulatory agencies and other health authorities.
- IRBs and IECs.

Investigator's personal information may be retained, processed, and transferred by Takeda and these other parties for research purposes including the following:

- Assessment of the suitability of investigator for the study and/or other clinical studies.
- Management, monitoring, inspection, and audit of the study.
- Analysis, review, and verification of the study results.
- Safety reporting and pharmacovigilance relating to the study.
- Preparation and submission of regulatory filings, correspondence, and communications to regulatory agencies relating to the study.
- Preparation and submission of regulatory filings, correspondence, and communications to regulatory agencies relating to other medications used in other clinical studies that may contain the same chemical compound present in the study medication.
- Inspections and investigations by regulatory authorities relating to the study.
- Self-inspection and internal audit within Takeda, its affiliates, and licensing partners.
- Archiving and audit of study records.
- Posting investigator site contact information, study details and results on publicly accessible clinical trial registries, databases, and websites.

Investigator's personal information may be transferred to other countries that do not have data protection laws that offer the same level of protection as data protection laws in investigator's own country.

Investigator acknowledges and consents to the use of his or her personal information by Takeda and other parties for the purposes described above.

Appendix E Ambulatory Blood Pressure Monitoring

The ambulatory BP recording device provided by the sponsor has been validated independently by the American Association for the Advancement of Medical Instrumentation. The device is an automatic, portable monitor that will be used to record BP and heart rate over a 24-hour period on two occasions during the study per the Schedule of Assessments, Appendix A.

The ABPM studies should be performed under similar circumstances (eg, a working weekday) if possible, and the device should be applied on the same day of the week and as close to the same time of day as feasible on each occasion. The non-dominant arm should be used for all ABPM readings. For each evaluation, the subject should report to the clinic for ABPM placement by 0800 am (±2 hours). Calibration should be performed per the ABPM Training Manual.

The ABPM recorder will be manually initiated to indicate the beginning of the test and the start time will be recorded in the eCRF and source document. The time of the in-clinic dose of study medication will also be recorded in the eCRF and source document. The device will be set to obtain readings every 15 minutes during the interval of 0600 to 2200 (to coincide with the daytime, awake period) and every 20 minutes during the interval of 2200 to 0600 (to coincide with the night time, sleeping period). Refer to the ABPM Training Manual for specific set-up requirements.

The subject should engage in their usual physical activity levels, but should avoid strenuous exercise during the monitoring period. Additionally, sleeping during the daytime (eg, a siesta) should be avoided during the ABPM study period. During the actual BP measurements, the subject should be instructed to hold their arm still and remain in place once cuff inflation begins.

Following completion of the 24-hour collection period, subjects should be instructed to return to the clinic site to return the ABPM equipment. The data collected should be verified by the investigator or designee to ensure adequate data collection. An ABPM recording will be considered of sufficient quality (pass) if:

- The "Beginning of Test" time is between 0600 and 1000.
- The monitoring period is at least 24 hours in duration.
- A minimum of 80% of the BP readings expected during the 24-hour period is recorded.
- There are no more than 2 non-consecutive hours with less than 1 valid BP reading, and 0 consecutive hours with less than 1 valid BP reading.

If any of the ABPM measurements do not pass these quality control criteria, they may be repeated once as long as the subject has an adequate supply of medication (placebo run-in /double-blind treatment) to resume treatment until the repeat measure can be taken.

For the Baseline (pre-randomization) and Final (week 8/early termination) ABPM recordings it is preferable, but not mandatory, that recordings satisfy the predefined quality control criteria before moving on to the next study step. ABPM readings for the Baseline (pre-randomization) and Final (week 8/early termination) if repeated, must be completed within 3 days.

In all cases of repeat ABPM recordings, only 1 repeat is permitted. Clinic vital signs should be collected whenever repeat ABPM measurements are taken.

Appendix F Detailed Description of Amendments to Text

Page 2, Section 1.1: Contacts

Existing Text

Issue	China Contact
Serious adverse event and pregnancy reporting	Quintiles Integrated Safety Management Lifecycle Safety Contact details: See Study Reference Materials
medical advice on protocol, compound, and medical	Quintiles Medical Services Department Contact details: See Study Reference Materials PPD

Revised Text

[figure not shown]
Issue	China Contact
Serious adverse event and pregnancy reporting	Quintiles Integrated Safety Management Lifecycle Safety Contact details: See Study Reference Materials
Medical Monitor (medical advice on protocol, compound, and medical management of subjects) Responsible Medical Officer (carries overall responsibility for the conduct of the study)	Quintiles Medical Services Department Contact details: See Study Reference Materials PPD

Rational for Amendment

To update the name of and contact information for the Responsible Medical Officer.

Page 3, Section 1.2: Approval

Existing Text

Rationale for Amendment

To update the names and titles for the Takeda signatories.

Page 14, Study Summary (paragraph 1)

Existing Text

The primary endpoint is change from baseline to Week 8 in trough (22-24 hour after the previous dose) sitting clinic SBP.

Revised Text

The primary endpoint is change from baseline to Week 8 in trough (**approximately 24 hours** after the previous dose) sitting clinic SBP.

Rationale for Amendment

To be consistent with the required timing of blood pressure measurements stated in Section 9.1.5 (Vital Sign Procedures).

Page 14, Study Summary: Main Criteria for Evaluation and Analyses, Efficacy

Existing Text

Change from baseline in trough sitting clinic SBP and DBP; percentage of responders; and percentage of subjects achieving target blood pressure at other study visits.

Revised Text

Change from baseline in trough sitting clinic SBP and DBP; percentage of responders; and percentage of subjects achieving target blood pressure at other study visits.

Change from Baseline to Week 8 in the following ABPM parameters (in a subgroup): 24 hour mean SBP and DBP; trough (22-24 hours after dosing) SBP and DBP; mean daytime (6 AM-10 PM) SBP and DBP; mean nighttime (12 AM-6 AM) SBP and DBP; mean SBP and DBP at 0-12 hours after dosing; peak (SBP and DBP) effect.

Trough-to-peak ratios (SBP and DBP) as determined by ABPM (in a subgroup).

Rationale for Amendment

For clarity.

Page 15, Study Summary: Statistical Considerations, Analysis Sets

Existing Text

Safety Analysis Set: All subjects who receive at least 1 dose of double-blind study medication. Subjects will be analyzed according to the study medication they received.

Full Analysis Set (FAS): All randomized subjects who received at least 1 dose of study medication. Subjects will be analyzed according to the treatment group to which they were randomized.

Revised Text

Safety Analysis Set: All subjects who receive at least 1 dose of double-blind study medication. Subjects will be analyzed according to the study medication they received.

Full Analysis Set (FAS): All randomized subjects who received at least 1 dose of study medication. Subjects will be analyzed according to the treatment group to which they were randomized

Subjects who were randomized more than once will be excluded from both the safety analysis set and the FAS.

Rational for Amendment

For clarity.

Page 21, Section 4.3: Summary of Clinical Data (paragraph 4)

Existing Text

TAK-491 dose reduction is not necessary for subjects with mild or moderate hepatic impairment, although such subjects are excluded from the present study.

Revised Text

Steady-state total exposures to TAK-536 after multiple doses of TAK-491 in a phase 1 hepatic impairment study were approximately 28% and 64% greater in subjects with mild and moderate hepatic impairment, respectively, than in healthy subjects. Subjects with severe hepatic impairment were not studied. The increases in exposure to TAK-536 in the phase 1 hepatic impairment study are not considered to be clinically meaningful as TAK-491 was well-tolerated in other pharmacokinetic studies in which exposures to TAK-536 were greater than those observed in subjects with hepatic impairment. Therefore, TAK-491 dose reduction is not necessary for subjects with mild or moderate hepatic impairment, although subjects with any degree of hepatic impairment are excluded from the present study.

Rational for Amendment

To add clinical data from the phase 1 hepatic impairment study to support the addition of Week 2 clinical laboratory tests.

Page 21, Section 4.3: Summary of Clinical Data (paragraph 5)

Existing Text

The single dose phase 1 study in renal impaired subjects showed that after 40 mg TAK-491 dosing, the total exposure to TAK-536 tended to be higher in subjects with renal impairment than in healthy subjects with increases of 30%, 25%, 96%, and 5% in subjects with mild, moderate, or severe renal impairment, and end-stage renal disease (ESRD), respectively. These increases in exposure to TAK-536 are not considered to be clinically meaningful, as TAK-491 was well-tolerated in a high-dose (160 to 320 mg) study in healthy subjects. The mean terminal elimination half-life (T1/2) of TAK-536 was not substantially different in subjects with renal impairment than in healthy subjects. Therefore, no dose adjustment of TAK-491 is required for subjects with any degree of renal impairment or ESRD, although subjects with severe renal impairment (estimated glomerular filtration rate [eGFR] <30 (mL/min/1.73 m²) are excluded from this study.

Revised Text

The single dose phase 1 study in renal impaired subjects showed that after 40 mg TAK-491 dosing, the total exposure to TAK-536 tended to be higher in subjects with renal impairment than in healthy subjects with increases of 30%, 25%, **95%**, **and 4%** in subjects with mild, moderate, or severe renal impairment, and end-stage renal disease (ESRD), respectively. These increases in

exposure to TAK-536 are not considered to be clinically meaningful, as TAK-491 was well-tolerated in a high-dose (160 to 320 mg) study in healthy subjects (01-06-TL-491-017). The mean terminal elimination half-life ($t_{1/2z}$) of TAK-536 was not substantially different in subjects with renal impairment than in healthy subjects. Therefore, no dose adjustment of TAK-491 is required for subjects with any degree of renal impairment or ESRD, although subjects with severe renal impairment (estimated glomerular filtration rate [eGFR] <30 (mL/min/1.73 m²) are excluded from this study.

Rationale for Amendment

To report total exposure for subjects with renal impairment as AUC_{∞} instead of AUC_{last} . The abbreviation for half-life was updated to the current Takeda standard.

Page 22, Section 4.3: Summary of Clinical Data (paragraph 7)

Existing Text

Results of the phase 3 program demonstrated that, relative to placebo, the TAK-491 20, 40, and 80 mg doses produce clinically and statistically significant reductions in systolic blood pressure (SBP) and diastolic blood pressure (DBP), as assessed by both ambulatory blood pressure monitoring (ABPM) and clinic blood pressure measurements. The differences between doses were greater for subgroups of subjects characterized by more severe and/or resistant hypertension, including black subjects, subjects with renal impairment, and subjects with *essential* hypertension. In each study, most of the blood pressure-lowering effect of TAK-491 was observed within 2 weeks of treatment; a plateau of effect was generally reached by week 4 and reductions were maintained through week 6 in short-term studies and over the long-term in two 6-month studies (and up to 1 year in open-label studies). In replicate studies, TAK-491 at 80 mg was shown to reduce systolic blood pressure more effectively than olmesartan medoxomil 40 mg and valsartan 320 mg, the highest approved doses in the US.

Revised Text

Results of the phase 3 program demonstrated that, relative to placebo, the TAK-491 20, 40, and 80 mg doses produce clinically and statistically significant reductions in systolic blood pressure (SBP) and diastolic blood pressure (DBP), as assessed by both ambulatory blood pressure monitoring (ABPM) and clinic blood pressure measurements. The differences between doses were greater for subgroups of subjects characterized by more severe and/or resistant hypertension, including black subjects, subjects with renal impairment, and subjects with **Grade 2** hypertension. In each study, most of the blood pressure-lowering effect of TAK-491 was observed within 2 weeks of treatment; a plateau of effect was generally reached by week 4 and reductions were maintained through week 6 in short-term studies and over the long-term in two 6-month studies (and up to 1 year in open-label studies). In replicate studies, TAK-491 at 80 mg was shown to reduce systolic blood pressure more effectively than olmesartan medoxomil 40 mg and valsartan 320 mg, the highest approved doses in the US.

Rationale for Amendment

To correct the text.

Page 23, Section 4.3: Summary of Clinical Data (paragraph 10)

Existing Text

In summary, TAK-491 was well tolerated at doses up to 320 mg in healthy subjects and up to 80 mg in hypertensive subjects (maximal dose evaluated in this population). TAK-491 has been shown to have a strong antihypertensive effect, predictable pharmacokinetic and metabolic profiles, a prolonged duration of action, and good safety and tolerability profiles when administered as a monotherapy to hypertensive subjects. TAK-491 has recently been approved in the United States (US) by the Food and Drug Administration (FDA), by the European Medicines Agency (EMA) in the European Union, and in other countries such as Canada, Switzerland. Mexico, Philippines for the treatment of hypertension, either alone or in combination with other antihypertensive agents.

Revised Text

In summary, TAK-491 was well tolerated at doses up to 320 mg in healthy subjects and up to 80 mg in hypertensive subjects (maximal dose evaluated in this population). TAK-491 has been shown to have a strong antihypertensive effect, predictable pharmacokinetic and metabolic profiles, a prolonged duration of action, and good safety and tolerability profiles when administered as a monotherapy to hypertensive subjects. As of February 2016, TAK-491 has been approved for the treatment of hypertension, either alone or in combination with other antihypertensive agents, in a total of 59 countries worldwide, including approval in the United States by the Food and Drug Administration (FDA) in February 2011 and in the European Union by the European Medicines Agency (EMA) in December 2011.

Rationale for Amendment

To present current registration information.

Page 24, Section 5.2.1: Primary Endpoint

Existing Text

The primary endpoint is change from baseline to Week 8 in trough (22-24 hour after the previous dose) sitting clinic SBP.

Revised Text

The primary endpoint is change from baseline to Week 8 in trough (**approximately 24 hours** after the previous dose) sitting clinic SBP.

Rationale for Amendment

To be consistent with the required timing of blood pressure measurements stated in Section 9.1.5 (Vital Sign Procedures).

Page 27, Section 6.1: Figure 6.a Schematic of Study Design (footnote [i])

Existing Text

(i) In subgroup of ABPM subjects will start 24-hour ABPM measurement.

Revised Text

(i) Visit 4 only applies to ABPM subgroup subjects; start 24-hour ABPM measurement.

Rationale for Amendment

To clarify that this visit applies only to the ABPM subgroup of subjects.

Page 27, Section 6.2: Justification for Study Design, Dose, and Endpoints

Existing Text

TAK-491 is a prodrug that is rapidly hydrolyzed to the active moiety, TAK-536, which is a long-acting, angiotensin II AT1 receptor blocker (ARB). TAK-491 has been shown to have a strong antihypertensive effect, predictable pharmacokinetic and metabolic profiles, a prolonged duration of action, and good safety and tolerability profiles when administered as a monotherapy to hypertensive subjects. The phase 3 TAK-491 studies have shown that TAK-491 80 mg reduced blood pressure more effectively than olmesartan medoxomil 40 mg and valsartan 320 mg, the highest approved doses in the US. TAK-491 has recently been approved in the US by FDA, by the EMA in the European Union, and in other countries, such as Canada, Switzerland, Mexico, Philippines for the treatment of hypertension, either alone or in combination with other antihypertensive agents.

Revised Text

TAK-491 is a prodrug that is rapidly hydrolyzed to the active moiety, TAK-536, which is a long-acting, angiotensin II AT1 receptor blocker (ARB). TAK-491 has been shown to have a strong antihypertensive effect, predictable pharmacokinetic and metabolic profiles, a prolonged duration of action, and good safety and tolerability profiles when administered as a monotherapy to hypertensive subjects. The phase 3 TAK-491 studies have shown that TAK-491 80 mg reduced blood pressure more effectively than olmesartan medoxomil 40 mg and valsartan 320 mg, the highest approved doses in the US. As of February 2016, TAK-491 has been approved for the treatment of hypertension, either alone or in combination with other antihypertensive agents, in a total of 59 countries worldwide, including approval in the United States by the Food and Drug Administration (FDA) in February 2011 and in the European Union by the European Medicines Agency (EMA) in December 2011.

Rationale for Amendment

To present current registration information.

Page 33, Section 7.4: Diet, Fluid, and Activity Control (paragraph 3)

Existing Text

Subjects will be instructed to fast for at least 8 hours prior to returning to the study site for Day 1 (Visit 5), Week 4 (Visit 7), and Week 8/ET (Visit 9).

Revised Text

After informed consent is provided, subjects will be asked to fast prior to blood draws within the Screening Period and will be instructed to fast for at least 8 hours prior to returning to the study site for Day 1 (Visit 5), Week 2 (Visit 6), Week 4 (Visit 7), and Week 8/ET (Visit 9).

Rationale for Amendment

To state that after informed consent is provided, that subjects will be asked to fast prior to blood draws within the Screening Period as certain serum chemistry test results are not accurate unless the subject has fasted.

To add a fasting requirement for Week 2 (Visit 6); the fasting requirement for Week 2 (Visit 6) is due to the addition of clinical laboratory tests at this Visit.

Page 37, Section 8.1.3: Dose and Regimen (paragraphs 4 and 5)

Existing Text

Placebo Run-in Period (Day -14 [Visit 2] to Day -1)

- Subjects will be dispensed one 2-week blister card and one bottle.
- Subjects will receive single-blind placebo tablets and placebo capsules.
- First dose will be given in-clinic at Day -14 (Visit 2).
- The daily oral administered dose will be one tablet from a blister card and two capsules from the bottle.

Treatment Period (Day 1 [Visit 5] through Week 8 / Early Termination [Visit 9])

- Subjects will receive blinded study medication and will be instructed to take their blinded study medication prior to their first meal of the day. Subjects will be dispensed one 2-week carton and one bottle at day 1 (Visit 5), at week 2 (Visit 6), week 4 (Visit 7), and week 6 (Visit 8).
- First dose will be given in-clinic at Day 1 (Visit 5).
- The daily oral administered dose will be one tablet from a blister card and two capsules from the bottle.

Revised Text

Placebo Run-in Period (Day-14 [Visit 2] to Day -1)

• Subjects will be dispensed one 2-week blister card and one bottle.

CONFIDENTIAL

- Subjects will receive single-blind placebo tablets and placebo capsules.
- First dose will be given in-clinic at Day -14 (Visit 2).
- The daily oral administered dose will be **two tablets** from a blister card and two capsules from the bottle.

Treatment Period (Day 1 [Visit 5] through Week 8 / Early Termination [Visit 9])

- Subjects will receive blinded study medication and will be instructed to take their blinded study medication prior to their first meal of the day. Subjects will be dispensed one 2-week carton and one bottle at day 1 (Visit 5), at week 2 (Visit 6), week 4 (Visit 7), and week 6 (Visit 8).
- First dose will be given in-clinic at Day 1 (Visit 5).
- The daily oral administered dose will be **two tablets** from a blister card and two capsules from the bottle.

Rationale of Amendment

To correct typographical errors.

Page 38, Section 8.1.4: Overdose (paragraph 3)

Existing Text

In the event of drug overdose, the subject should be treated symptomatically. Elimination of TAK-491 by dialysis or hemoperfusion has not been examined. Valsartan cannot be removed from the plasma by hemodialysis [22].

Revised Text

In the event of drug overdose, the subject should be treated symptomatically. **Hemodialysis does not significantly remove TAK-536 or M-II from the systemic circulation.** Valsartan cannot be removed from plasma by hemodialysis [22].

Rationale for Amendment

To add results from the TAK-491 phase 1 renal impairment study.

Page 43, Section 9.1.7: Documentation of Concurrent Medical Conditions (paragraph 2)

Existing Text

Continuous Positive Airway Pressure (CPAP) data will be collected during the study. If CPAP is ongoing at the time of informed consent, this data will be captured on the concurrent medical conditions (e)CRF. If CPAP is administered after first dose of study drug administration, then this will be captured as an AE.

Revised Text

Data on medical conditions that require Continuous Positive Airway Pressure (CPAP) will be collected during the study. If CPAP is ongoing at the time of informed consent, **the medical condition that required CPAP** will be captured on the concurrent medical conditions (e)CRF. If CPAP is administered after first dose of study drug, then **the medical condition** will be captured as an AE.

Rationale for Amendment

For clarity.

Pages 43-44, Section 9.1.8: Procedures for Clinical Laboratory Samples (paragraph 1, Table 9.a and paragraph 2)

Existing Text

All samples will be collected in accordance with acceptable laboratory procedures. The maximum volume of blood at any single visit is approximately 40 mL, and The approximate total volume of blood for the study is 185 mL. Subjects will be instructed to fast for at least 8 hours prior to blood draws on Day 1 (Visit 5), Week 4 (Visit 7), and Week 8/ET (Visit 9). Details of these procedures and required safety monitoring will be given in the laboratory manual.

Table 9.a Clinical Laboratory Tests

Hematology	Serum Chemistry	Urinalysis
Hemoglobin	Albumin	Specific gravity
